9.2. Vital signs

Vital signs will be measured by a qualified staff member at Visit 1, Visit 2 prior to randomization, Visit 4 (cohort 1 ONLY) prior to treatment and at Visit 8. The following items will be measured:

- Body temperature
- Pulse rate
- Respiration rate

- Blood pressure (systolic and diastolic) after the subject sits quietly for at least 5 minutes
- Height (at Visit 1 only)
- Weight (at Visit 1 only).

Any measure that is, in the opinion of the investigator, abnormal AND clinically relevant (CR) must be recorded as history if found prior to the first study medication treatment or as an AE if found after the first study medication treatment begins (Section 10.1).

A systolic blood pressure >140mm Hg or a diastolic blood pressure >90mm Hg is considered abnormal and therefore must be defined as CR or not clinically relevant (NCR) on the CRFs.

9.3. Clinical laboratory sampling

Non-fasting blood samples for clinical laboratory analysis will be collected by a qualified staff member at Visit 1 and at Visit 8. Approximately 7.5 mL of blood will be collected for each chemistry sample and 3ml of blood will be collected for the complete blood count (CBC). These blood samples will be sent to a central laboratory for analysis. Refer to the study specific laboratory manual for instructions regarding handling of the blood samples and shipping instructions.

The following tests, at a minimum, will be conducted:

Chemistry Panel	Complete Blood Count
Albumin	Hematocrit
Alkaline phosphatase	Hemoglobin
Alanine aminotransferase (ALT)	Platelet count
Aspartate aminotransferase (AST)	Red blood cell morphology
Blood urea nitrogen (BUN)	Red blood cell count
Bicarbonate	White blood cell count
Calcium	White blood cell differential
Chloride	% & absolute
Creatinine	Basophils
Glucose	Eosinophils
Lactate dehydrogenase (LDH)	Lymphocytes
Phosphorus	Monocytes
Potassium	Neutrophils
Sodium	
Total bilirubin	
Total protein	
Uric acid	

The results of the clinical laboratory tests will be reported on the central laboratory's standard reports. These laboratory results will be sent to the investigator via fax/email. The investigator must review all laboratory reports in a timely manner and note NCS or CS to define the clinical significance of any result that is outside the normal range for the laboratory. The investigator must date and initial every laboratory report.

The investigator must review the Visit 1 laboratory results for all the measured analytes for each subject prior to Visit 2. The subject must not be enrolled to the study at Visit 2 if any of the Visit 1 results are outside normal range for the laboratory AND, in the opinion of the investigator, CS.

The investigator must report all laboratory results that are BOTH outside the normal range for the laboratory AND, in the opinion of the investigator, CS as medical history if found prior to the first study medication treatment or as an AE if found after the first study medication treatment begins.

9.4. Urine pregnancy tests

The investigator or designee will perform a urine pregnancy test for subjects who are WOCBP (Section 11) at Visit 1, at Visit 2 prior to randomization and at Visit 8.

Subjects who are WOCBP must have a negative pregnancy test result at Visit 1 to continue in the study and at Visit 2 to be randomized.

If the result of any post-randomization urine pregnancy test is positive, the subject will be withdrawn from the study and the subject's pregnancy documented and followed (Section 11).

9.5. Other Evaluations

9.5.1. Demographics and medical history

At Visit 1, the investigator or designee will collect demographic information including date of birth, sex at birth, race and, if appropriate, ethnicity for each subject.

At Visit 1, the investigator must determine each subject's Fitzpatrick skin type and document appropriately on the subject's CRF.

Table 7 Fitzpatrick Skin Type Scoring System

Skin Type Classification	Description
Type I	always burns, never tans
Type II	usually burns, tan less than average (with difficulty)
Type III	sometimes mild burn, tan about average
Type IV	rarely burn, tan more than average (with ease)
Type V	very rarely burns, tans very easily
Type VI	never burns, never tans

(Fitzpatrick, 1988)

Medical history information will be recorded including all medical conditions and disease states that, at Visit 1:

- Are ongoing

- Require concomitant therapy
- Are, in the opinion of the investigator, relevant to the subject's study participation.

10. ADVERSE EVENTS

10.1. Definitions

10.1.1. Adverse events (AE)

An adverse event (AE) is any untoward medical occurrence in a patient that develops or worsens in severity during the conduct of a clinical study of a pharmaceutical product and does not necessarily have a causal relationship to the study drug. An adverse event can, therefore, be any unfavorable and unintended physical sign, symptom, or laboratory parameter that develops or worsens in severity during the course of the study, or significant worsening of the disease under study (or any concurrent disease), whether or not considered related to the study drug.

- Accordingly, an adverse event could include any of the following:
- intercurrent illnesses
- physical injuries
- events possibly related to concomitant medication
- significant worsening (change in nature, severity, or frequency) of the disease under study or other pre-existing conditions. (NOTE: A condition, recorded as pre-existing, that is intermittently symptomatic [e.g., headache] and which occurs during the study should be recorded as an adverse event.)
- drug interactions
- events occurring during diagnostic procedures or any washout phase of the study
- laboratory or diagnostic test abnormalities occurring after the start of the study (i.e., after screening and once confirmed by repeat testing) that results in the withdrawal of the patient from the study, requires medical treatment or further diagnostic work-up, or is considered by the study investigator to be clinically significant. NOTE: Abnormal laboratory test results at the screening visit that preclude a patient from entering the study or receiving study treatment are not considered adverse events, but will be recorded to monitor data from patients who do not meet screening criteria.

Worsening of any of the Target Lesion assessments should be reported as an AE ONLY if the use of the study medication is interrupted or discontinued or if therapy is required to manage the event.

The investigator must, for any Target Lesion related AE, question the subject in detail to determine if there are any confounding factors (e.g., irritation by clothing or activity, sunburn) for any such AE.

The investigator should, when certain, report a diagnosis rather than the signs, symptoms or clinically relevant abnormal laboratory values associated with the AE. Otherwise, signs, symptoms or abnormal laboratory values may be used to describe the AE.

Any CR abnormality discovered prior to the first study medication treatment should be reported as medical history, not as an AE.

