While there are existing methods for treating DPN lesions, many require specialized training and the use of expensive equipment, they are often quite painful and may require anesthesia and/or analgesia, and they are often complicated by significant adverse cosmetic outcomes. Both hypopigmentation and hyperpigmentation, which may be transient but is often permanent, are common, particularly when cryosurgery is employed and particularly in individuals of the darker skin types prone to develop DPN. The potential for scarring at the treatment site, particularly with the surgical treatment options, and the typical post-surgical risks of bleeding and infection increase the risk that the sequela from the treatment of these benign, but cosmetically disturbing, lesions may be worse than the lesions themselves. There is a great unmet need for a safe, effective, standardized and less painful treatment for this extremely common condition in patients of darker skin types.

Hydrogen peroxide (H_2O_2) is a compound that is ubiquitous in the environment. It is the simplest peroxide and a potent oxidizing agent commonly used in innumerable household goods including chlorine-free bleaches, general-purpose cleaning products, and disinfectants. Additionally, H_2O_2 has been employed as the oxidizing component in hair dyes and has been used in oral hygiene products and tooth-whitening systems for many years. In industry, it is employed in the treatment of wastewater. In high concentrations, it is used in bleaching paper, pulp, and textiles. Clinically, in addition to its use as an oral topical agent noted above, H_2O_2 is widely employed at low concentrations (e.g., 3%-6%) as a wound irrigant and topical antiseptic/disinfectant and has been in use medicinally since its introduction into clinical practice by Richardson in 1858.

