¹⁵A-101 study medication will be applied by the treating physician. All Target DPN Lesions will be treated with study medication following enrollment at Visit 2. Subjects randomized to ARM B will be required to have their Target DPN Lesions medically abraded prior to treatment with A-101 study medication. If a Target DPN Lesion meets the criteria for re-treatment as defined in Section 7.5, the lesion will be re-treated at Visit 3, and Visit 5. Following application of study medication, subjects must NOT wash/submerge the Target DPN Lesions for at least 6 hours and they must NOT apply any topical products to the Target DPN Lesions for at least 6 hours.

¹⁶All subjects will be required to apply Aquaphor to all Target DPN Lesions the morning after study medication application. Sites will be provided supplies of Aquaphor by the Sponsor.

¹⁷All concomitant therapies including (topical and oral) prescription medications, over the counter medications and natural supplements and non-drug therapies including chiropractic, physical therapy, and energy-based therapy must be documented in the subject CRF. Subjects must not apply any topical products (e.g. moisturizers, sunscreen, etc.) to their Target Lesions within 12 hours prior to any study visit.

¹⁸The reporting period for Serious Adverse Events (SAEs) begins when the subject signs the informed consent. Refer to Section 10 for instructions on the reporting of SAEs. Non-serious clinical adverse events will be collected following the application of the study medication at Visit 2. Non-serious adverse events that occur between the time of consent and study medication application will be documented as medical history. All safety reporting (AEs and SAEs) will conclude at Visit 5 (approximately 21 days after last study medication application) except for clinical adverse events related to local skin reactions. These events will be collected through V8.

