9.1. Local Skin Reactions (LSR)

The LSR assessment is the investigator's assessment of the signs and the subject's assessment of the symptoms associated with irritation at each Target DPN Lesion site, which includes the Target DPN Lesion and the area immediately surrounding the Target DPN Lesion.

Local Skin Reactions:

- Signs (assessed by the investigator):
 - Erythema
 - Edema
 - Scaling/dryness
 - Vesicles/bullae
 - Crusting
 - Erosion
 - Ulceration
 - Post-inflammatory hyper-pigmentation
 - Post-inflammatory hypo-pigmentation (does not include the superficial transient skin blanching/whitening related to the action of the study medications)
 - Atrophy
 - Scarring.
- Symptoms (assessed by the subject):
 - Stinging/burning
 - Pruritus (itch).

At Visits 2-8, the investigator and the subject will evaluate the LSR signs and the LSR symptoms at each Target DPN Lesion site respectively.

The investigator will assess the LSR signs as follows:

- Visits 2 and 4 (cohort 1) and Visits 2, 3 and 5 (cohort 2):
 - For each Target DPN Lesion site report the severity for all signs prior to any study medication treatment

- For every treated Target DPN Lesion site, 20 (\pm 4) minutes after the Treatment Completion Time, report the severity for the following signs:
 - Erythema
 - Edema
 - Scaling/dryness
 - Vesicles/bullae
- Visits 3 and 5-8 (cohort 1) and Visits 4 and 6-8 (cohort 2):
 - For each Target DPN Lesion site, report the severity for all signs.

The subject will assess the LSR symptoms as follows:

- Visits 2 and 4 (cohort 1) and Visits 2, Visit 3 and Visit 5 (cohort 2):
 - For each Target DPN Lesion site report the average of the severity over the previous 24 hours for all symptoms prior to any study medication treatment
 - For every treated Target DPN Lesion site, 10 (\pm 4) minutes after the Treatment Completion Time, report the average of the severity of the LSR for all symptoms since completion of the study medication treatment.
- Visits 3 and 5-8 (cohort 1) and Visits 4 and 6-8 (cohort 2):
 - For each Target DPN Lesion site, report the average of the severity over the previous 24 hours for all symptoms.

Both the subject and the study staff member will initial and date the source document to indicate the subject performed the LSR for symptoms as instructed. The staff member must not influence the subject's assessment.

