10.2. Reporting Procedures

10.2.1. Procedures for reporting adverse events

At each post enrollment visit, the investigator or designee will question the subject to elicit AEs using a non-directive question such as “Has there been any change in your health since the previous study visit?”

The investigator or designee will monitor the subject for at least 20 minutes after the Treatment Completion Time at Visit 2 and at Visit 4 to elicit AEs in a similar manner.

If appropriate, based on the subject's response to non-directed questioning regarding AEs, the investigator or designee will follow-up with directed questions and appropriate evaluations.

Any AE noted during the reporting period must be reported in the source documents and on the appropriate AE CRF.

AEs that are defined as “Not Related” to the study medications will be followed until they are resolved or until the subject’s last study visit. AEs that are defined as “Related” to the study medications will be followed until they are resolved or, if not resolved after the subject’s last study visit, until in the opinion of the investigator, the AE reaches a clinically stable outcome with or without sequelae.

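### If the target-lesion AE rule covers skin reactions, untreated pigment change, atrophy or scarring after the last application gets no AE status, causality rating or follow-up past Visit 8; the AE windows also conflict.

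*Protocol*

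**What the plan says.** Protocol 10.1.1 first defines an AE broadly. It includes "any unfavorable and unintended physical sign, symptom, or laboratory parameter that develops or worsens in severity during the course of the study". It then restricts one class of event. Where any of the Target Lesion assessments worsens, that change "should be reported as an AE ONLY if the use of the study medication is interrupted or discontinued or if therapy is required".

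Protocol 9.1 lists the investigator-graded LSR signs at each target lesion site. They include "Post-inflammatory hyper-pigmentation", hypopigmentation, atrophy and scarring. All are graded 0 to 3 at Visits 2 to 8. SAP 3.7.2 tabulates LSRs by subject and by lesion, at each visit and as the maximum over visits.

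Protocol 10.2.1 follows Related AEs beyond the last study visit, if unresolved, until in the investigator's opinion "the AE reaches a clinically stable outcome with or without sequelae". Not Related AEs are followed until resolution or the last visit.

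The collection period is stated in several ways:

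- **Footnote 18 of both schedules (Protocol 6, repeated in SAP 2.1):** all AE and SAE reporting ends at Visit 5, "except for clinical adverse events related to local skin reactions. These events will be collected through V8".
- **The Adverse Events row of the same schedules:** marked to Visit 6.
- **Protocol 10.1.3 and SAP 2.4.3.2:** non-serious AEs to Visit 6, with no exception for skin reactions.
- **SAP 3.7.3:** an AE is treatment-emergent if it is new or worse between the first treatment and 30 days after the last.

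**The concern.** The restriction has two limbs. The first needs study medication that can still be interrupted or discontinued, and after the last application there is none. Only the therapy limb remains, so whether a scar or pigment change becomes an AE would depend on whether someone treats it.

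This matters because of the protocol's own case for the product. Protocol 2.1 says of existing treatments: "Both hypopigmentation and hyperpigmentation, which may be transient but is often permanent, are common", particularly in the darker skin types prone to DPN. Safety in Fitzpatrick types 5 and 6 is part of the primary objective (3.2.1). Exclusion criterion 4 refers to post-inflammatory hyperpigmentation lasting more than 1 year, so the plan recognises that such change can outlast the trial. If these signs are not AEs, AE incidence and relatedness leave them out, and nothing asks whether those present at the last visit later settle.

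**Working it through.** There is no plan figure to reproduce. The check sets the passages side by side and does the day arithmetic from the visit schedules, counting all windows from Day 1.

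1. **Does the restriction reach LSR signs?** The term is undefined. The sentence tests for interruption of medication or need for therapy, and the next one tells the investigator to ask about irritation by clothing or activity and about sunburn. Both fit local reactions better than a lesion-severity score. I take the wider reading as more natural, but the text does not settle it.

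2. **When does the first limb lapse?** The last possible application is Visit 4 in cohort 1 (Day 22, window +4) and Visit 5 in cohort 2 (Day 29, window +4). Visit 8 is Day 106 ± 7, that is Day 99 to 113.
   - Cohort 1: 106 − 22 = 84 days of observation after the last application (range 99 − 26 = 73 to 113 − 22 = 91).
   - Cohort 2: 106 − 29 = 77 days (range 99 − 33 = 66 to 113 − 29 = 84).
   - A subject treated on Day 1 only: 106 − 1 = 105 days.

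3. **What happens to an untreated, non-serious sign in that period?** Under the wider reading it meets neither limb. Footnote 18 collects skin-reaction AEs to Visit 8 but gives no other threshold for a reaction to become an AE. The sign keeps its LSR grade. Protocol 9.1 asks for severity only, so there is no causality rating.

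4. **Does anything else follow it past Visit 8?** Follow-up after the last visit is written for Related AEs (10.2.1), SAEs (10.2.2) and subjects withdrawn because of an AE (5.4, 10.2.3). None covers an LSR sign that was never an AE.

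5. **Would a qualifying late event reach the AE tables?** Treatment-emergent window:
   - Cohort 1: 22 + 30 = Day 52, at the latest 26 + 30 = Day 56.
   - Cohort 2: 29 + 30 = Day 59, at the latest 33 + 30 = Day 63.
   - Earliest Visit 7: 78 − 7 = Day 71.

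   The window closes at least 71 − 63 = 8 days before any Visit 7. An event with onset at Visit 7 or 8 falls outside the SAP 3.7.3 summaries even if therapy was given.

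6. **Does footnote 18 fit the schedule?** It places Visit 5 about 21 days after the last application. In cohort 1 the nominal gap is 29 − 22 = 7 days. In cohort 2 Visit 5 is itself the third application day.

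**The case against.** The strongest reply is that the restriction may not apply to these signs. The named lesion assessment is the physician's efficacy scale in Protocol 8, while LSRs sit in Section 9 and are scored at the lesion site, which includes surrounding skin. If only efficacy measures are meant, a new scar or pigment change is an AE under the general definition and, if Related, is followed to stability. Footnote 18 fits that reading, since it expects skin-reaction AEs after dosing has ended. This stands as a real ambiguity. It does not remove the problem, because two investigators could apply the rule differently and both be within the text.

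It is also fair to say that the safety data exist. The four signs are graded through Visit 8, the lesions are photographed, and LSR grades are tabulated. A dedicated scale with an AE threshold is a legitimate design, and any trial of fixed length leaves some signs unresolved at its last visit. A reader might infer that pigment change goes unrecorded; the documents do not support that.

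Two other inferences are tempting. One is that these signs appear late and usually go untreated, so that hardly any would become AEs. No passage says so; Protocol 2.1 speaks of how common and lasting pigment change is after other treatments, not of onset or management. The other is to read 84 of 105 days (80%) and 77 of 105 (73%) as the share of events lost. Those are calendar days on which one limb cannot operate. The therapy limb operates throughout, and SAEs remain reportable.

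**Conclusion.** The point holds as a gap in classification and follow-up. It depends on reading the restriction to include LSR signs. On that reading, an untreated, non-serious pigment change, atrophy or scar after the last application has no AE status, no causality rating and no follow-up past Visit 8. On the narrower reading that gap largely closes, but the undefined term still needs settling.

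The conflict between AE windows holds on either reading and needs no assumption about the signs. Collection ends at Visit 5, 6 or 8 depending on the passage, and the treatment-emergent window shuts before Visit 7 in both cohorts.

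The number of events affected cannot be derived from the documents. The ceiling is 36 subjects with up to 4 lesions each, 36 × 4 = 144 lesions. The change is worth making because the signs are central to the safety question and the remedy is small.

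**What to change.** 1. In Protocol 10.1.1, define the target lesion assessments that the restriction covers, and say whether LSR signs are among them.
2. In the same section, state that hyperpigmentation, hypopigmentation, atrophy or scarring at a target lesion site is recorded as an AE with a causality rating, whether or not therapy is given, if it is worse than the Visit 2 pre-treatment grade and present at Visit 8 or the subject's last visit. If Related, it is followed under 10.2.1. Including the last visit covers subjects who leave early.
3. Reconcile footnote 18, Protocol 10.1.3, the Adverse Events row of both schedules and SAP 2.4.3.2, so that these events are collected through Visit 8. Without this, step 2 creates AEs after collection has closed.
4. In SAP 3.7.3, report these events on a separate line not limited to the 30-day treatment-emergent window. Otherwise they are collected and then left out.

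The cost is protocol and SAP wording, a few more AEs and some follow-up contacts after Visit 8. Transient irritation stays out of the AE tables. If subject visits are already complete, a listing of lesions meeting the step 2 condition can still be drawn from the LSR data, but it supplies neither causality nor outcome.

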10.1.2. Serious adverse event (SAE)

A Serious Adverse Event is any untoward medical occurrence that at any dose:

- Results in death
- Is life threatening
- Requires inpatient hospitalization or prolongation of existing hospitalization
- Results in persistent or significant disability/incapacity, or
- Is a congenital anomaly/birth defect
- Is an important medical event.

The term “life threatening” refers to an event in which the subject was at risk of death at the time of event; it does not refer to an event that hypothetically might have caused death if it was more severe.

Inpatient hospitalization is considered to have occurred if the subject is admitted to the hospital on an in-patient basis, even if released the same day. Prolongation of hospitalization is defined as an additional night stay in the hospital. Hospitalization for a diagnostic test (even if related to an AE) or elective hospitalization that was planned before study enrollment (signing the ICF) are not themselves reasons for an event to be defined as a SAE.

Important medical events are those that may not be immediately life threatening, result in death or hospitalization, but are clearly of major clinical significance and may jeopardize the subject or require intervention to prevent one of the outcomes listed in the SAE definition above. These should also usually be considered serious. Examples of such events are intensive treatment in an emergency room or at home for allergic bronchospasm, blood dyscrasia or convulsions that do not result in hospitalization.

